13.2.4. Renal Monitoring Plan

- **Serum Cystatin C:** GFR is a requisite component of renal testing to evaluate glomerular and nephron integrity. While “gold standard” methods of determining GFR (eg, infusions of inulin, iohexol, iohalamate, or technetium 99m-diethylenetriamine pentaacetic acid [^{99m}Tc-DTPA] with timed blood and urine assessments) can be employed, these methods are cumbersome and are often reserved for renal physiology laboratories at specialized centers [Guignard 2004, Stevens 2007]. In clinical practice, assessments of GFR have more typically relied upon determination of creatinine clearance during 24-hour urine collections or calculation based on nomograms using only serum creatinine. It is generally acknowledged that 24-hour urine collection in children is inaccurate and impractical due to compliance issues [Guignard 2004]. Calculation of GFR using only measurement of serum creatinine has long been standardized for children [Schwartz 1987]. However, because it is both filtered and secreted by the kidney, serum creatinine is acknowledged to be relatively imprecise and insensitive marker of renal damage [Herget-Rosenthal 2007, Schwartz 2007]. Moreover, serum creatinine is subject to variation based on endogenous and exogenous factors. This problem is particularly concerning in boys with DMD because the majority of creatinine in serum is derived from muscle [Wang 1996] and boys with DMD have decreased serum creatinine concentrations due to reduced muscle mass. A review of baseline serum creatinine values among the 38 boys with DMD participating in the ataluren Phase 2a study indicates low serum creatinine values (median 0.3, range 0.1-0.5 mg/dL). Additional sources of variability for boys with DMD may include ingestion of creatine (a substrate for creatinine production) [Escobar 2005] and treatment-mediated alterations in muscle fragility [Mendell 1989].

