As an alternative to assessing GFR based on serum creatinine, serum cystatin C offers substantial advantages in the context of this protocol. Cystatin C is a low-molecular-weight [~13 kDa] proteinase inhibitor derived from all cells that is filtered by the glomerulus and degraded in the renal tubules [Herget-Rosenthal 2007]. The serum cystatin C concentration is almost solely dependent upon GFR and appears relatively unaffected by muscle mass or other conditions. An additional advantage is that circulating cystatin C changes more rapidly in response to multiple types of renal injury than creatinine [Herget-Rosenthal 2007]. Methods for measuring cystatin C are standardized and the correlations between serum cystatin C and GFR have been derived and confirmed in large studies involving healthy children and adults and those with renal dysfunction [Dharnidharka 2002, Grubb 2005, Zappitelli 2007]. Based on these considerations, values of serum cystatin above 1.33 mg/L should prompt diagnostic evaluation and interruption/modification of study drug if required per protocol.

- **Serum Creatinine:** Given the widespread clinical familiarity with serum creatinine as a marker of renal dysfunction and as a monitoring tool for nephrotoxins in clinical practice [Gilead 2002, Gilead 2006, Novartis 2005], characterization of serum creatinine provides an appropriate frame of reference relative to other experiences. Because most participating boys with DMD are expected to have low normal values of serum creatinine due to reduced muscle mass, any values higher than the normal range may be cause for concern. Caveats regarding interpretation of serum creatinine in boys with DMD (particularly if there are

food- or treatment-induced changes in serum creatinine values) dictate that an increase in serum creatinine above the age-specific normal range should prompt reevaluation of other safety parameters and potential interruption/modification of study drug dosing.

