Traditional methods of urine protein screening are only semiquantitative, are relatively insensitive, and are confounded by exogenous substances and subjective interpretation [Kim 2007]. The presence of urinary protein may be masked in dilute urine or exaggerated in concentrated urine. For these reasons, a quantitative method of accessing proteinuria is planned in this study. Two methods will be assessed: urinary protein concentration relative to urinary creatinine concentration [Ginsberg 1983, Schwab 1987] and urinary protein concentration relative to urine osmolality [Wilson 1993, Morgenstern 2003]. These methods of screening, using spot urine samples, have been found to be as accurate as and more practical than quantification of urine protein during a 24-hour collection. Values for protein:creatinine of ≥ 0.2 mg/dL:mg/dL and of protein:osmolality of ≥ 0.15 mg/L:mOsm/kg have been established as abnormal [Morgenstern 2003]. While measurement of protein:creatinine is generally the preferred method in children [Morgenstern 2003], it is possible that low urinary creatinine excretion in boys with DMD may falsely elevate protein:creatinine ratios. For this reason, confirmed evidence that both measures are

abnormal should stimulate further evaluation and intervention. Follow-up methods such as urine electrophoresis may be useful in discriminating among the types of proteins present and may suggest a site of injury (eg, an albumin-specific pattern with glomerular damage versus a diffuse multiple low-molecular-weight protein pattern with tubular damage) [Stevens 2007]. Confirmed proteinuria should prompt consideration of interruption/modification of study drug dosing.

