13.2.5. Hepatic Monitoring Plan

Muscle breakdown results in ALT and AST values that are commonly 10- to 20-fold > ULN (Grade 3-4) in patients with DBMD. Consequently, it is not practical to exclude patients with high serum AST or ALT concentrations from enrollment in this study, and monitoring for hepatotoxicity must rely primarily on following patients for increases in bilirubin or GGT. Consistent with well-established guidelines [Abboud 2007] applied in this disease setting, even modest (Grade 2) alteration in bilirubin or GGT values should prompt interruption of study drug. While serum ALT or AST values cannot routinely serve as measures of hepatic injury in boys with DBMD, significant increases in ALT (>150 U/L) in conjunction with a stable or falling CK should prompt increased frequency of laboratory monitoring and possibly an evaluation for potential hepatotoxicity.

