### **5.7.2. Laboratory Tests**

Hematological, serum biochemistry, adrenal laboratories, and urine data and their changes (only for continuous laboratory parameters) from baseline will be summarized by visit.

Shift tables for hematology and biochemistry data will also be presented showing change in CTCAE severity grade from baseline to each visit. For parameters for which a CTCAE scale does not exist, shift tables will be presented showing change in results from baseline (normal, low and high [or abnormal]) to each visit (normal, low and high [or abnormal]).

Summary of abnormalities in laboratory variables pre-defined for safety monitoring will be done per the following Table 2.

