**Table 2: Safety Monitoring Parameters and Actions to be Taken**

Organ System and Laboratory Parameter	Stop Study Drug Immediately, Confirm Abnormal Value, and Then Start Work-Up	Stop Study Drug After Confirming a Abnormal Value, and Then Start Work-Up	Continue Study Drug, Confirm Abnormal Value, and then Start Work-Up a
Hepatic			
Serum total bilirubin	≥Grade 3 (≥3.0 x ULN)	Grade 2 (1.5 – 3.0 x ULN)	---
Serum GGT	≥Grade 3 (≥5.0 x ULN)	Grade 2 (>2.5 – 5.0 x ULN)	---
Serum ALT			↑ of >150 U/L with stable or ↓ CK
Renal			
Serum cystatin C	>2.00 mg/L	>1.33 – 2.00 mg/L	---
Serum creatinine	≥Grade 2 (≥1.5 x ULN for age)	Grade 1 (>ULN – 1.5 x ULN for age)	---
Serum BUN	≥3.0 x ULN	≥1.5 – 3.0 x ULN	---
Urine protein: urine creatinine (spot)	---	>0.40 mg:mg	---
Urine protein: urine osmolality (spot)	---	>0.30 mg/L:mOsm/kg	---
Urine blood (by dipstick)	4+ (Large)	3+ (Moderate)	2+ (Small)
Serum electrolytes	Grade 3-4	Grade 2	Grade 1
Serum Na + , high	>155 mmol/L	>150 – 155 mmol/L	---
Serum Na + , low	<130 mmol/L	---	---
Serum K + , high	>6.0 mmol/L	>5.5 – 6.0 mmol/L	---
Serum K + , low	<3.0 mmol/L	---	---
Serum Mg 2+ , high	>1.23 mmol/L	---	---
Serum Mg 2+ , low	<0.4 mmol/L	<0.5 – 0.4 mmol/L	---
Total serum Ca 2+ , high	>3.1 mmol/L	>2.9 – 3.1 mmol/L	---
Total serum Ca 2+ , low	<1.75 mmol/L	<2.0 – 1.75 mmol/L	---
Serum phosphorous	<0.6 mmol/L	<0.8 – 0.6 mmol/L	---
Serum HCO 3 	<11 mmol/L	<16 – 11 mmol/L	---

a Laboratory abnormalities may be confirmed immediately or at the next scheduled clinic visit based on investigator judgment.

**Abbreviations:** ALT = alanine aminotransferase, BUN = blood urea nitrogen, Ca2+ = calcium, CK = creatine kinase, GGT = gamma glutamyl transferase, HCO3 = bicarbonate, K+ = potassium, Mg2+ = magnesium, Na+ = sodium, ULN = upper limit of normal

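### No planned laboratory table counts boys by change in creatinine, cystatin C or BUN from their own baseline, so a large creatinine rise that stays within normal limits goes uncounted

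*SAP*

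**What the plan says.** SAP section 5.7.2 plans three laboratory displays.

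- Values, and changes from baseline for continuous parameters, summarized by visit. Under SAP section 5.1 these summaries include the minimum and maximum.
- Shift tables: "Shift tables for hematology and biochemistry data will also be presented showing change in CTCAE severity grade from baseline to each visit". Other parameters are shown as low, normal or high: "For parameters for which a CTCAE scale does not exist, shift tables will be presented showing change in results from baseline".
- Counts against the monitoring limits: "Summary of abnormalities in laboratory variables pre-defined for safety monitoring will be done per the following Table 2". The lowest creatinine category in that table is "Grade 1 (>ULN – 1.5 x ULN for age". Cystatin C enters above 1.33 mg/L and BUN from 1.5 x ULN.

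Protocol section 13.2.4 describes where these boys start. Its review of the 38 Phase 2a participants "indicates low serum creatinine values (median 0.3, range 0.1-0.5 mg/dL", and for this trial it states that "most participating boys with DMD are expected to have low normal values of serum creatinine due to reduced muscle mass".

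SAP section 6.2 takes baseline at entry to the extension, so it follows the 48 weeks of Study 020.

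**The concern.** Laboratory abnormalities are part of the primary endpoint (SAP section 3.3), and the kidney is the organ for which the protocol sets up a specific monitoring plan. Protocol section 13.2.3 reports renal findings in mice with no level free of effect identified, and small mean rises in creatinine, BUN and cystatin C in Study 007.

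The protocol's own data put these boys well below the point at which a creatinine grade begins. A table that counts only values above ULN therefore cannot separate a boy who stays at 0.3 mg/dL from one who doubles. Rises of that kind, real for the individual but still within normal limits, are what a long-term safety extension should be able to count.

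**Working it through.** The documents give no figure to reproduce: there is no hypothesis (SAP section 3.4) and the paired t-tests were removed (SAP section 7). The check asks how far each marker can move before a planned table counts it.

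**Inputs.** From the documents: creatinine median 0.3, range 0.1 to 0.5 mg/dL; Grade 1 above ULN and Grade 2 from 1.5 x ULN; cystatin C limit 1.33 mg/L; BUN limit 1.5 x ULN; at most about 220 boys. Assumed, because the documents do not give them: creatinine ULN 0.5 to 1.0 mg/dL, baseline cystatin C 0.6 to 1.0 mg/L, baseline BUN 0.5 to 1.0 x ULN.

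**Step 1, creatinine.** Largest fold rise with no shift and no Table 2 creatinine entry = ULN / baseline.

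| Assumed ULN (mg/dL) | from 0.1 | from 0.3 | from 0.5 |
|---|---|---|---|
| 0.5 | 5.0 | 1.67 | 1.0 |
| 0.6 | 6.0 | 2.0 | 1.2 |
| 0.7 | 7.0 | 2.33 | 1.4 |
| 0.8 | 8.0 | 2.67 | 1.6 |
| 1.0 | 10.0 | 3.33 | 2.0 |

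Reaching Grade 2 from 0.3 takes 1.5 x 0.5 / 0.3 = 2.5-fold to 1.5 x 1.0 / 0.3 = 5.0-fold.

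**Step 2, by-visit means.** If 11 of 220 boys (5%) go from 0.3 to 0.7 mg/dL, the mean change moves by 11 x 0.4 / 220 = 0.02 mg/dL.

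**Step 3, cystatin C.** Fold rise to the Table 2 limit = 1.33 / baseline: 1.33 / 0.6 = 2.2 down to 1.33 / 1.0 = 1.3. A boy who doubles from 0.6 to 1.2 mg/L is not in the Table 2 row. A shift table would show him only if the laboratory's upper reference limit lies below 1.2, and the documents do not state that limit.

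**Step 4, BUN.** Fold rise to the Table 2 limit = 1.5 x ULN / baseline: 1.5 / 0.5 = 3.0 down to 1.5 / 1.0 = 1.5. A normal-to-high shift would need 1.0 / 0.5 = 2.0-fold from half the ULN.

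**Step 5, the remaining displays.** The by-visit maximum shows one extreme value per visit, and listings show raw data. Neither gives a number of boys. SAP section 5.7.1 counts laboratory abnormalities reported as adverse events, but protocol section 8.1.1 keeps those needing no intervention or further investigation out of adverse event reporting. The worst-grade display in protocol section 10.4.3 is grade-based, so it has the same blind spot.

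**The case against.** The strongest reply is that the protocol knows creatinine is unreliable in DMD and adds cystatin C for that reason. A reader might infer that a halved GFR would go unseen. The documents do not support that. If cystatin C varies inversely with GFR, halving GFR doubles it, and any boy starting above 1.33 / 2 = about 0.67 mg/L enters the Table 2 row. Over the assumed 0.6 to 1.0 mg/L only the lowest starters escape. BUN, urine protein and urine blood rows add further coverage. What remains is smaller rises, low starters and the absence of any count relative to a boy's own baseline.

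A reader might also extend the point to the liver, since "Muscle breakdown results in ALT and AST values that are commonly 10- to 20-fold > ULN (Grade 3-4) in patients with DBMD". That does not hold. Table 2 has bilirubin and GGT rows, the markers on which protocol section 13.2.5 mainly relies. It also has an ALT rule based on change: a rise above 150 U/L with stable or falling CK. With an assumed ALT ULN of 30 to 50 U/L and a baseline of 10 to 20 x ULN, that is between 150 / (20 x 50) = 15% and 150 / (10 x 30) = 50% of baseline. Stable CK is undefined and AST has no row, but hepatic change is largely covered. Plain ALT, AST or CK ratios would bring back the muscle confounding that the rule limits.

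A third inference is that the Table 2 summary counts pre-existing abnormality as arising on study. The SAP does not say so; it is silent on boys beyond a limit at entry. The question is still live, because the protocol notes that "it is possible that low urinary creatinine excretion in boys with DMD may falsely elevate protein:creatinine ratios", although it looks for both urine protein ratios to be abnormal for that reason.

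Finally, the extension baseline is on ataluren for boys who received it in Study 020. The Study 007 renal rises tended to level off early, so similar rises may already sit in that baseline. A simple ratio or baseline flag would hide them. This objection stands, and it shapes the fix.

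**Conclusion.** The point holds for renal markers. No table in SAP section 5.7.2 counts boys by creatinine, cystatin C or BUN change from their own baseline. From the documented median creatinine, a rise of about 1.7- to 3.3-fold is not counted on the creatinine scale; from 0.5 mg/dL the figure is about 1.0- to 2.0-fold. Cystatin C and BUN narrow the gap without closing it.

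These sizes rest on an assumed ULN of 0.5 to 1.0 mg/dL and on 38 Phase 2a boys; Study 020e baselines are not in the documents. This is a gap in how a component of the primary endpoint is reported, in a descriptive study without tests. It is not evidence that renal harm would be missed altogether.

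**What to change.** In SAP section 5.7.2, add the number (%) of boys by maximum post-baseline ratio to baseline (>=1.5x, >=2x, >=3x) for serum creatinine, cystatin C and BUN.

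- Show it by prior arm (ataluren/ataluren, placebo/ataluren), the grouping that SAP section 5.8.4 already uses for loss of ambulation. For ataluren/ataluren boys, also give the ratio to the pre-ataluren Study 020 baseline. Patient numbers carry over from Study 020 (protocol section 5.2), so the records can be linked.
- Read creatinine >=2x together with cystatin C. If creatinine is reported to 0.1 mg/dL (an assumption), a single step from 0.1 to 0.2 is already a 2-fold ratio.
- In the Table 2 summary, show boys already beyond a limit at extension baseline separately, by prior arm. Do not label abnormalities that arose on ataluren in Study 020 as not treatment-emergent.

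No stopping limit changes, and all three markers are already measured at every visit. The cost is one added table, a baseline flag, the link to Study 020 values, and some rounding noise at the lowest creatinine values.

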**Table 2: Safety Monitoring Parameters and Actions to be Taken**

Organ System and Laboratory Parameter	Stop Study Drug Immediately, Confirm Abnormal Value, and Then Start Work-Up	Stop Study Drug After Confirming a Abnormal Value, and Then Start Work-Up	Continue Study Drug, Confirm Abnormal Value, and then Start Work-Up a
Hepatic			
Serum total bilirubin	≥Grade 3 (≥3.0 x ULN)	Grade 2 (1.5 – 3.0 x ULN)	---
Serum GGT	≥Grade 3 (≥5.0 x ULN)	Grade 2 (>2.5 – 5.0 x ULN)	---
Serum ALT			↑ of >150 U/L with stable or ↓ CK
Renal			
Serum cystatin C	>2.00 mg/L	>1.33 – 2.00 mg/L	---
Serum creatinine	≥Grade 2 (≥1.5 x ULN for age)	Grade 1 (>ULN – 1.5 x ULN for age)	---
Serum BUN	≥3.0 x ULN	≥1.5 – 3.0 x ULN	---
Urine protein: urine creatinine (spot)	---	>0.40 mg:mg	---
Urine protein: urine osmolality (spot)	---	>0.30 mg/L:mOsm/kg	---
Urine blood (by dipstick)	4+ (Large)	3+ (Moderate)	2+ (Small)
Serum electrolytes	Grade 3-4	Grade 2	Grade 1
Serum Na + , high	>155 mmol/L	>150 – 155 mmol/L	---
Serum Na + , low	<130 mmol/L	---	---
Serum K + , high	>6.0 mmol/L	>5.5 – 6.0 mmol/L	---
Serum K + , low	<3.0 mmol/L	---	---
Serum Mg 2+ , high	>1.23 mmol/L	---	---
Serum Mg 2+ , low	<0.4 mmol/L	<0.5 – 0.4 mmol/L	---
Total serum Ca 2+ , high	>3.1 mmol/L	>2.9 – 3.1 mmol/L	---
Total serum Ca 2+ , low	<1.75 mmol/L	<2.0 – 1.75 mmol/L	---
Serum phosphorous	<0.6 mmol/L	<0.8 – 0.6 mmol/L	---
Serum HCO 3 	<11 mmol/L	<16 – 11 mmol/L	---

a Laboratory abnormalities may be confirmed immediately or at the next scheduled clinic visit based on investigator judgment.

**Abbreviations:** ALT = alanine aminotransferase, BUN = blood urea nitrogen, Ca2+ = calcium, CK = creatine kinase, GGT = gamma glutamyl transferase, HCO3 = bicarbonate, K+ = potassium, Mg2+ = magnesium, Na+ = sodium, ULN = upper limit of normal

## 5.8. Other Variables

### 5.8.1. Vital Signs

Vital signs (systolic and diastolic blood pressure, pulse rate, body weight, height, ulna length, arm span, and body temperature) will be summarized by visit for overall subjects.

Number (%) of subjects with meeting hypertension criteria as the following will be summarized.

- If age <18 years old, the hypertension criteria are based on age, gender, and height-adjusted systolic blood pressure (SBP) and diastolic blood pressure (DBP) percentile results (Hypertensive:  $\geq$  95th percentile; Pre-hypertensive: 90 - < 95th percentile; Normal: < 90th percentile).
- If age  $\geq$  18 years old, hypertensive: SBP  $\geq$  140 mmHg or DBP  $\geq$  90 mmHg; pre-hypertensive: SBP 120 - 139 mmHg or DBP 80 - 89 mmHg; Normal: SBP 90 - 119 mmHg and DBP 60 - 79 mmHg.

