6.2. Study Drug Treatment

6.2.1. Duration of Treatment

In this study, treatment will comprise continuous daily treatment with ataluren for up to 144 weeks (~3 years). This study may be further extended by amendment until either ataluren becomes commercially available or the clinical development of ataluren in DMD is discontinued.

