7.5. Height, Weight, and Physical Examination

Standing height (in cm) will be measured at Screening/Baseline on Visit 1, Week 12 (Visit 2), Week 24 (Visit 3), Week 36 (Visit 4), Week 48 (Visit 5), Week 60 (Visit 6), Week 72 (Visit 7), Week 84 (Visit 8), Week 96 (Visit 9) Week 108 (Visit 10), Week 120 (Visit 11), Week 132 (Visit 12), Week 144 (Visit 13- End-of-Treatment/Premature Discontinuation), and at the Post-Treatment visit (6 weeks post discontinuation of study drug).

For nonambulatory patients, due to the difficulty in obtaining an accurate standing height measurement, ulna length and arm span will be used as a surrogate measure for height (see Study Manual). Ulna length and arm span (in cm) will be measured at Screening/Baseline on Visit 1, Week 12 (Visit 2), Week 24 (Visit 3), Week 36 (Visit 4), Week 48 (Visit 5), Week 60 (Visit 6), Week 72 (Visit 7), Week 84 (Visit 8), Week 96 (Visit 9) Week 108 (Visit 10), Week 120 (Visit

11), Week 132 (Visit 12), Week 144 (Visit 13 - End-of-Treatment/Premature Discontinuation), and at the Post-Treatment visit (6 weeks post discontinuation of study drug).

Weight (in kg) will be measured at Screening/Baseline on Visit 1, Week 12 (Visit 2), Week 24 (Visit 3), Week 36 (Visit 4), Week 48 (Visit 5), Week 60 (Visit 6), Week 72 (Visit 7), Week 84 (Visit 8), Week 96 (Visit 9) Week 108 (Visit 10), Week 120 (Visit 11), Week 132 (Visit 12), Week 144 (Visit 13- End-of-Treatment/Premature Discontinuation), and at the Post-Treatment visit (6 weeks post discontinuation of study drug).

A full physical examination (including evaluation of cardiovascular system, chest and lungs, thyroid, abdomen, nervous system, skin and mucosae, musculoskeletal system, eyes, ears, nose, mouth, throat, spine, lymph nodes, extremities, and genitourinary) will be conducted at Screening/Baseline (Visit 1), Week 48 (Visit 5), and Week 96 (Visit 9) and Week 144 (Visit 13 – End of Treatment/Premature Discontinuation) visit.

Physical exams may also be performed at any time during the study as clinically indicated.

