10.4.3. Primary Variables – Safety

Vital signs (height, weight, systolic and diastolic blood pressure, radial pulse rate, and body temperature) and physical examination data will be listed and summarized by visit and overall. Where appropriate, changes from baseline at each visit will be summarized and tested by means of the paired t-test or a nonparametric alternative.

Adverse events will be classified using the MedDRA classification system. The severity of adverse events will be graded according to the CTCAE, Version 3.0, whenever possible.

The frequency of patients experiencing a specific adverse event will be tabulated by treatment period and for the whole study, categorizing events by body system, and MedDRA term. In the by-patient analysis, a patient having the same event more than once will be counted only once. Adverse events will be summarized by worst CTCAE grade within a patient.

Adverse events classified as CTCAE Grade 3 or higher; study-drug-related events; adrenal, hepatic, and renal events leading to special diagnostic evaluations; events leading to discontinuation from treatment; and SAEs will be considered with special attention.

No attempt will be made to reconcile data collected from the patient/caregiver-reported outcome instruments with adverse event reporting.

Hematological data will be summarized by treatment period and overall. Hematological data will be graded according to CTCAE severity grade. The frequencies of the worst severity grade observed will be displayed by worst CTCAE grade within a patient.

Serum biochemistry and urine data (including parameters for assessment of adrenal, hepatic, and renal monitoring – see [Section 6.3.1](#)) will be summarized by treatment period and overall. Values will be graded according to CTCAE severity grade, when applicable. For variables graded according to CTCAE severity grade, the frequencies of the worst severity grade observed will be displayed within a patient. For parameters for which a CTCAE scale does not exist, the frequency of patients with values below, within, and above the normal ranges will be summarized.

Urinalysis data will be listed and summarized by treatment period and overall, and will be checked for changes from baseline over time.

The results of an ultrasound to examine the kidneys and collecting system will be listed and abnormal results will be noted and investigated in terms of their relation to other relevant patient outcome measurement.

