13.2.8. Other Nonclinical Findings

Single lipomatous, non-metastatic tumors, determined to be malignant hibernomas originating in brown adipose tissue were identified in 6 rats during a 26 week toxicity study. In a second 26 week rat study, no malignant hibernomas were observed in any dose group, including the high dose group (1200 mg/kg/day). The exact correlative relevance of this finding is unclear given the lack of reproducibility in rats, the different physiology of brown fat in rats relative to humans [Cannon 2004, Iatropoulos 2004], the very young age of the rats used in these studies, the lack of ataluren genotoxicity, and the extreme rarity and generally benign course of hibernomas in humans [Furlong 2001].

Urinary bladder tumors were observed in 3/60 females at the high dose of 300 mg/kg/day in the 24-month carcinogenicity study in rats. This dose exceeded the maximum tolerated dose (MTD), based on an average 23% reduction in body weight gain in comparison to vehicle controls throughout the study. In addition, the proposed mode of urinary bladder tumor formation (presence of calculi) in rats is not considered relevant to humans. Mean steady state exposures in

female rats at the mid-dose of 100 mg/kg/day and in male rats at the high-dose of 300 mg/kg/day were 4 and 6 times, respectively, the steady state exposure in patients administered ataluren at the morning, midday and evening doses of 10, 10 and 20 mg/kg/day, respectively.

Long-term post-treatment follow-up safety data currently available from the patients dosed with ataluren to date in the clinical studies, some for over 7 years indicate no increased risk of tumors.

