In the event of an inhibition of body height increases that is unacceptable to the patient/family, the following interventions are recommended:

- Corticosteroid dosage should not be increased to adjust for increases in body weight
- Reassurance and support should be provided. Counseling from a child psychologist should be considered.
- If the failure to gain height remains unacceptable to child/family, dosage reductions of ≤ 5 mg total dose for prednisone (≤ 6 mg total dose for deflazacort) at ~6-8-week intervals can be considered.
- Every attempt should be made to avoid stopping corticosteroids solely for failure to gain height; if the patient/family demands that corticosteroids be stopped, see [Section D](#) below for procedures for withdrawal of corticosteroids.

Hyperglycemia or Glycosuria

Evidence of fasting hyperglycemia or $\geq 1+$ glycosuria persisting for ≥ 6 weeks should prompt the following interventions:

- Institute monitoring of glycosylated hemoglobin (hemoglobin A1c) to evaluate for evidence of chronic hyperglycemia.
- If hyperglycemia or glucosuria is only episodic and chronic hyperglycemia is not present by hemoglobin A1c, corticosteroids should not to be increased to adjust for increases in body weight.
- If chronic hyperglycemia is present by hemoglobin A1c, consultation should be arranged with an endocrinologist regarding diagnostic evaluation and potential intervention for hyperglycemia
- If hyperglycemia persists and corticosteroid dose reduction is warranted, dosage reductions of ≤ 5 mg total dose for prednisone (≤ 6 mg total dose for deflazacort) at ~ 6 -8-week intervals can be considered.
- If the endocrinologist recommends corticosteroid discontinuation, corticosteroids may be stopped. See [Section D](#) below for procedures for withdrawal of corticosteroids.

Hypertension

Evidence of substantial hypertension (blood pressure elevation at 99th percentile for age) persisting for ≥ 6 weeks should prompt the following interventions:

- Corticosteroids should not to be increased to adjust for increases in body weight. Dietary recommendations (weight reduction/sodium reduction) should be considered.

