#### **Safety**

- Change from baseline in other safety parameters (eg, vital signs)

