## 5.3. Demographic and Baseline Characteristics

Subject demographic and disease characteristics (age, age group (6-11, 12-17, and  $\geq 18$  years), gender, race, ethnicity, height, weight, body mass index, six minute walk distance, six minute walk distance groups ( $<300$  meters,  $\geq 300$ - $<400$  meters,  $\geq 400$  meters), time to run/walk 10 meter, time to stand from supine, time to stand from supine ( $<5s$ ,  $\geq 5s$ ), performance of Upper Limb Assessment (PUL), corticosteroid use (Yes/No), and ambulatory/non-ambulatory) at study entry will be summarized for overall subjects, a subgroup of subjects with corticosteroid use duration ( $<12$  months,  $\geq 12$  months) at baseline, a subgroup of subjects with corticosteroid type (deflazacort vs prednisone/prednisolone) at baseline, and a subgroup of ambulatory/non-ambulatory subjects at study entry.

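### SAP 5.8.1 summarises height and weight by visit only, with neither change from baseline nor an age-standardised growth measure, so its tables cannot separate normal growth from slowed growth or excess weight gain

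*SAP*

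**What the plan says.** Protocol 6.2.1 plans "continuous daily treatment with ataluren for up to 144 weeks (~3 years"). Protocol 7.5 and the Schedule of Events call for height and weight at all 14 visits. For boys who cannot walk, protocol 7.5 states that "ulna length and arm span will be used as a surrogate measure for height".

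The planned post-baseline analysis is in SAP 5.8.1: "pulse rate, body weight, height, ulna length, arm span, and body temperature) will be summarized by visit for overall subjects". SAP 5.1 would otherwise display data by baseline ambulatory status, but 5.8.1 asks for all subjects together. The pooled ages are wide: SAP 5.3 uses "age group (6-11, 12-17, and" 18 years or over. BMI appears in 5.3 only, as a study-entry characteristic.

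Two other places expect more than a by-visit summary:
- SAP 3.3 lists as a safety endpoint "Change from baseline in other safety parameters (eg, vital signs").
- Protocol 10.4.3 counts height and weight among the vital signs and says: "Where appropriate, changes from baseline at each visit will be summarized and tested by means of the paired t-test or a nonparametric alternative".

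SAP 6.3 defines absolute and relative change from baseline. SAP section 7 removes the supportive 6-minute walk analyses and all paired t-tests; it does not mention removing the change summaries. For blood pressure in patients under 18, SAP 5.8.1 does standardise, using percentiles adjusted for age, sex and height.

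**The concern.** Most of these boys are expected to be growing. A by-visit mean of height or weight mixes expected growth with any departure from it, and the tables contain nothing that shows what growth to expect at each boy's age. Raw change from baseline is needed to deliver the SAP's own endpoint, but it would not remove normal growth either.

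Who is measured also changes. If standing height is not taken once a boy stops walking, the height mean at later visits comes from those still walking. Protocol 2.1 says most boys use a wheelchair by 10 to 14 years, so the boys lost from the height row will tend to be older and taller. That pulls the mean down while growth pushes it up, and the visit means cannot then be read as growth in either direction.

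The subject matters in this population. Protocol Appendix A manages growth problems under corticosteroids, beginning "In the event of an inhibition of body height increases that is unacceptable to the patient/family", and has a parallel entry for weight gain. At stake is whether a long-term pediatric safety report can say anything about growth at group level.

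**Working it through.** **Reading the SAP for growth analyses.** The plan has no figure to reproduce: the sample size is not based on a hypothesis, and no growth rate or SD is given. The check is which sections carry out change from baseline.

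| Place | Change from baseline stated? | Age-standardised? |
|---|---|---|
| SAP 3.3, safety endpoint (vital signs) | Yes, as an endpoint | No |
| SAP 5.7.2, laboratory | Yes | Not applicable |
| SAP 5.8.3 to 5.8.8, function and spirometry | Yes | %-predicted for FVC and FEV1 |
| SAP 5.8.1, blood pressure under 18 | No | Yes, percentiles |
| SAP 5.8.1, height, weight, ulna length, arm span | No | No |

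So the endpoint in 3.3 has no matching instruction in 5.8.1, and growth is left raw in the section that standardises blood pressure.

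**Illustration of size.** Follow-up is from protocol 6.2.1. The growth rates and SDs are assumptions, given as ranges.

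1. Follow-up: 144 × 7 / 365.25 = 1008 / 365.25 = 2.76 calendar years.
2. Normal height gain at an assumed 4-7 cm/year: 4 × 2.76 = 11.0 cm to 7 × 2.76 = 19.3 cm.
3. Velocity halved throughout: 0.5 × 11.0 = 5.5 cm to 0.5 × 19.3 = 9.7 cm. The mean still rises.
4. Velocity reduced by a quarter: 0.75 × 11.0 = 8.3 cm to 0.75 × 19.3 = 14.5 cm. This overlaps the normal range between 11.0 and 14.5 cm.
5. The same slowing as a height z-score, with an assumed SD for age of 6-8 cm held constant:
   - halved: 5.5 / 8 = 0.7 to 9.7 / 6 = 1.6 SD fall;
   - reduced by a quarter: 2.8 / 8 = 0.3 to 4.8 / 6 = 0.8 SD fall.
6. Weight at an assumed 2.5-4.5 kg/year: normal gain is 2.5 × 2.76 = 6.9 kg to 4.5 × 2.76 = 12.4 kg. A gain 50% above normal is 10.3 to 18.6 kg. The ranges overlap between 10.3 and 12.4 kg.
7. At Week 48: 336 / 365.25 = 0.92 year. Normal gain is 3.7-6.4 cm and halved gain 1.8-3.2 cm.

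In raw units, slowed growth is a smaller rise that must be judged against an unstated expectation. As a z-score it is a fall from the boy's own starting point, with an expected change near zero.

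**The case against.** The strongest reply is that change from baseline was never dropped. It is a named endpoint in SAP 3.3, it is defined in 6.3, section 7 does not remove it, and the SAP overrides the protocol only where the two conflict. This stands: 5.8.1 is better described as incomplete than as a decision to abandon the endpoint. It still needs correcting, because 5.8.1 is the instruction from which the tables would be built.

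A reader might infer that impaired growth would be reported as normal, or go unseen. The documents do not support that. The SAP does not classify growth at all. By-patient listings are planned for every CRF module, the tables carry SD, median and range, and abnormal vital signs reported as treatment-emergent events are counted. In the illustration, the normal and halved height ranges do not overlap, so a pediatric reader who knew the age mix might notice a large shortfall. A quarter reduction is harder to see, and the other routes depend on someone reading listings or an investigator reporting an event.

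A reader might also infer that the documents name growth suppression as an ataluren risk. They do not. Protocol 13.2.8 judged a rat dose to exceed the maximum tolerated dose, "based on an average 23% reduction in body weight gain in comparison to vehicle controls". That is weight, not height, at 300 mg/kg/day; exposure at that dose was 6 times the patient exposure in male rats, and already 4 times in females at 100 mg/kg/day. Appendix A concerns corticosteroids.

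Finally, surrogate height may not be available when needed. Protocol 7.5 introduces ulna length and arm span for nonambulatory patients, so a boy who loses ambulation on study may have no baseline surrogate. The spirometry plan's use of ulna length suggests wider measurement but does not settle the matter. If both surrogates are measured in every boy, the SAP already summarises two measures that do not depend on walking, and the changing-subset point weakens; the lack of standardisation remains.

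**Conclusion.** The point holds as a gap in the planned summary tables. SAP 5.8.1 does not carry out the change-from-baseline endpoint for height and weight, and no age-standardised growth measure appears in either document. Under an assumed 4-7 cm/year, halved growth over a full 144 weeks would still show as a rise of 5.5-9.7 cm, against 11-19 cm normally. Those figures rest on the assumed growth rates and on full follow-up; the sponsor ended the study early, so actual follow-up may be shorter and the amounts smaller.

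The primary endpoint, adverse events and laboratory abnormalities, is unaffected. A reader might expect z-scores to show harm from ataluren. They would not: with no control arm and corticosteroids in the background, they show departure from reference growth and leave its cause open. The change is worth making because it is cheap and completes an endpoint the SAP already lists.

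**What to change.** In SAP 5.8.1:

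- Add change from baseline by visit for height, weight, ulna length and arm span.
- Add height-, weight- and BMI-for-age z-scores by sex from one named reference, with within-boy change in z-score by visit. Use age on the measurement date, since the SAP 6.1 windows are mostly 84 days wide and the last is open-ended. State how patients above the reference's age limit are handled.
- Show these overall and by baseline corticosteroid use.
- Count boys whose z-score rises or falls by more than a prespecified amount. This is a reporting threshold and triggers no clinical action.
- Restrict paired height change to boys with the same measure (standing height or the same surrogate) at baseline and follow-up, and report n at each visit. If a surrogate is converted to height, name the equation.
- State that the results describe departure from reference growth and do not attribute it to ataluren.

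The cost is SAP wording, one derived dataset and the choice of a reference population. No single reference fits all participating countries well; using within-boy change limits that problem without removing it. No new visits or measurements are needed. Boys without a matching baseline measure drop out of the paired height analysis, which is why n must be shown.
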